**11.8 \* Data Analysis**

Describe method(s) of data analysis. Include the role of external collaborators as appropriate.

As per recommended by the food and drug administration (17), the hemagglutination inhibition (HI) antibody assay has been used to assess vaccine activity and may be appropriate for the evaluation of the pandemic influenza vaccine. Appropriate endpoints may include: 1) the percentage of subjects achieving an HI antibody titer  $\geq 1:40$ , and 2) rates of seroconversion, defined as the percentage of subjects with either a pre-vaccination HI titer  $< 1:10$  and a post vaccination HI titer  $> 1:40$  or a pre-vaccination HI titer  $\geq 1:10$  and a minimum four-fold rise in post-vaccination HI antibody titer. Previous study have built models using both HAI and neutralization assays to determine vaccine responsiveness.

The RNA-seq analysis will be run with the help of the Genome resource center as well as the expertise of [name] listed as a collaborator of this project.

**11.9 \* Explain the rationale for the choice of statistical measures and the number of subjects proposed for the study, including the power calculations when applicable.**

Since no preliminary data is available to estimate the percentage of participants achieving a determined level for the HI antibody titer and the rate of seroconversion for each group (healthy volunteers and metabolic syndrome participants) we provide an estimation of the minimum effect size for the sample size selected is able to detect. For a sample size of 40 participants, 20 at each group, a 95% significant Chi-square test will be able to detect an effect size equal or larger than 0.56 with 0.8 power. It means that a Chi-square test will be able to detect independence between groups if the distance between the observed odd ratio is larger than 1.56.

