**Statistical Analysis**

To compare the means of antibody titers between groups (healthy volunteers and metabolic syndrome participants) a t-test at 95% significance level will be performed if the data follows a normal distribution, otherwise a non parametric Wilcoxon-Mann-Whitney test will be used.

A Chi-square test at 95% significance level will be used for the comparison of percentage of participants achieving a determined level for the HI antibody titer and rates of seroconversion. On that case if any observed frequency is smaller than 5 Fisher exact test will be used instead of Chi-square.

Expression values will be modeled using mixed-effect models, with group as fixed factor, and a random effect for each participant. FCHs for the comparisons will be estimated, and hypothesis testing conducted.

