## 16.0 Recruitment and Advertising

**For assistance consult CRSO to create a robust Recruitment Plan see Help.**

### 16.1 \* What is the plan for recruitment?

**Overview:**

The CRROSS will prescreen up to 100 volunteers in order to enroll 20 with a metabolic syndrome and 20 healthy controls to achieve the goal of 40 evaluable participants at study completion. Healthy controls will be age matched (+/-5 years) and gender matched to the metabolic syndrome participants.

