**Projected enrollment timeline:** Recruitment initiation will begin as soon the study receives IRB approval, likely in the first or second week of November. The investigator's target of completing accrual by April 2016, which would allow for 5-6 months achieving complete study enrollment. This would require the enrollment of 10 participants (5 metabolic syndrome and 5 age matched controls) per month. The study requires 2 screening visits (1 week start-up lag). The enrollment timeline is ambitious, even assuming a steady flow of participants and likely only feasible using the Repository population and potentially expanding the age range. Based on previous recruitment experience of this population, CRROSS would predict 12- 15 months for study accrual, however given ResearchMatch and Repository resources, 6 months is ambitiously feasible.

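### Controls are matched on age and gender, but the planned titre comparison ignores both factors; if either affects titre, the test is conservative and gives up some power

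*Combined protocol and SAP*

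**What the plan says.** The matching appears only in the recruitment section. Section 16.1 (Overview) says: "Healthy controls will be age matched (+/-5 years) and gender matched to the metabolic syndrome participants". The projected enrollment timeline in the same section refers to "5 metabolic syndrome and 5 age matched controls" per month and mentions age only. Neither place says whether controls are paired one to one or balanced as a group. The sample codes in section 11.10 run in sequence within each cohort and carry no pair identifier.

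Section 11.9 sizes the study as two independent groups: "For a sample size of 40 participants, 20 at each group". For titres, the Statistical Analysis text says that "a t-test at 95% significance level will be performed if the data follows a normal distribution", and "otherwise a non parametric Wilcoxon-Mann-Whitney test will be used". For responder endpoints, "A Chi-square test at 95% significance level will be used for the comparison of percentage of participants achieving a determined level", with Fisher's exact test when an observed frequency is below 5. The expression model has a fixed effect for group and a random effect for participant. No section plans a paired test, a matched-set term, or an adjustment for age or sex.

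**The concern.** Matching on a factor that affects the outcome takes that factor's variation out of the difference between the groups. A two-sample test does not know this. It estimates its error from the whole within-group spread, including the part due to age and sex. The estimated standard error is then larger than the true one, and the test rejects less often than its nominal level allows.

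At stake is efficiency in a study of 40 that will be hard to enlarge. Section 16.1 reports that a similar population needed 325 prescreened people to enroll 28. The eligible age range is wide (18 to 65, section 12.1), so an age effect on titre is plausible, although the documents do not quantify one.

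**Working it through.** **Inputs from the documents.** There are 20 participants per group and a 5% level (sections 11.9, 12.7 and 16.1). Sidedness is not stated; two-sided is assumed. Matching is on age within 5 years and on gender (16.1). An earlier vaccine study lost 15 of 86 participants before its final visit (16.1).

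**Inputs assumed.** R² is the share of titre variance explained by age and sex, and the documents give no value. The range 0 to 30% is shown. With close matching, the correlation ρ between matched partners is about equal to R².

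**The plan's own figure.** Section 11.9 says a "Chi-square test will be able to detect an effect size equal or larger than 0.56 with 0.8 power". At N = 40, 1 df, two-sided 5% and 80% power, the noncentrality needed is N·w² = 7.85, so w = √(7.85/40) = 0.443. The stated 0.56 is not reproduced; w = 0.56 fits N of about 25. That is a separate matter, and nothing below rests on it.

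**Step 1: a reference effect.** For an unmatched two-sample t-test with 38 df, the noncentrality is d·√(n/2). Power of 80% at n = 20 needs d = 0.909, because 0.909 × √10 = 2.875.

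**Step 2: the standard error.** The two-sample test estimates SE = σ√(2/n). The true SE under matching is σ√(2(1−ρ)/n). The overstatement is 1/√(1−ρ), which is 1.00, 1.05, 1.12 and 1.20 for ρ = 0, 0.1, 0.2 and 0.3.

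**Step 3: type I error of the planned test.** The critical value 2.024 acts as if it were 2.024/√(1−ρ), that is 2.134, 2.263 and 2.420 for ρ = 0.1, 0.2 and 0.3. Referred to t with 38 df, these give 3.9%, 2.9% and 2.0%. Simulation gives 3.9%, 2.9% and 2.1%.

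**Step 4: power of the planned and the adjusted test.** Power of the planned test on matched data was simulated. The model adjusted for age and sex has 36 df and noncentrality d·√(10/(1−R²)), which is 2.875, 3.030, 3.214 and 3.436.

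| R² (assumed) | Planned t-test | Adjusted for age and sex | Difference |
|---|---|---|---|
| 0% | 80.1% | 79.9% | −0.2 |
| 10% | 81.2% | 83.9% | 2.7 |
| 20% | 82.5% | 87.8% | 5.3 |
| 30% | 83.9% | 91.7% | 7.8 |

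**Step 5: does the type of matching matter?** Simulated frequency matching (four age bands by sex) gave 81%, 82% and 84% unadjusted against 84%, 88% and 92% adjusted at R² of 10%, 20% and 30%. Type I error was 3.7%, 3.0% and 2.2%. The result does not depend on one-to-one pairs.

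**Step 6: is a strictly paired test the better remedy?** Not reliably. With 20 intact pairs, the paired t-test (19 df) has 77.9% power at ρ = 0 and overtakes the planned test only between ρ = 0.05 and 0.1. Dropout of 15/86 = 17.4% leaves about 20 × 0.826 = 16.5 per arm but only 20 × 0.826² = 13.6 complete pairs. At 14 pairs against 16 per arm, the two tests break even at ρ of about 0.2 (70.1% each). For responder rates of 0.72 against 0.28, exact McNemar has 69.6% power against 80.1% for chi-square at ρ = 0, and 80.2% against 83.0% at ρ = 0.2. It is ahead only at 0.3 (86.6% against 84.6%).

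**The case against.** The strongest reply is that the loss is conditional, modest and in the safe direction. At R² = 0 the planned standard error is correct. The planned test does not exceed 5% type I error, and in every row of the table it keeps at least the nominal 80% power. Matching also balances age and sex between the cohorts, a benefit that the unpaired comparison retains. All of this stands: the planned test is not invalid, and a reader who inferred that the effort of matching is wasted would go too far.

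The gain may also be smaller than the table suggests. Section 16.1 reports 17 potentially eligible repository volunteers aged 18 to 50 and 22 aged 51 to 59, predominantly male. An illustrative simulation (assumed ages 45 to 60, 80% one sex) used the coefficients that give R² of 10% and 20% over the full age range. Power was 83.2% planned against 83.8% adjusted, and 86.5% against 88.2%. A second simulation of a narrow, mostly one-sex sample put the gain at about 1 to 3 points. This stands as a limit on the size.

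A reader might infer from the 5-year caliper and the 20:20 allocation that each control is individually paired with a case. That is a natural reading, but the text never says so, and the sample codes show no pairs. Step 5 shows that the point does not need it.

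Finally, adjustment is harder to defend for the yes/no endpoints. In simulation with 40 participants, an ordinary logistic model with cohort, age and sex had type I error of 5.7% to 7.0%, and estimates diverged in about 5% to 16% of runs in the narrow, mostly one-sex setting. The objection is sound, and the fix below follows it.

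**Conclusion.** The mismatch is certain: the design matches on age and gender, and no planned analysis uses either. Its cost is conditional. If age and sex explain 10%, 20% or 30% of titre variance, the planned t-test runs at about 3.9%, 2.9% and 2.1% type I error and gives up about 3, 5 and 8 points of power at 20 per group. These figures assume a two-sided 5% level, a true difference of 0.909 SD, and an age and sex spread wide enough to produce that R². The documents support no particular value, so they do not support the reading that standard errors are too large as a matter of fact. The figures apply to continuous titre, not to the responder endpoints. This is a worthwhile and nearly free gain in efficiency, not a threat to validity.

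**What to change.** In section 11.9, make the primary titre comparison a linear model on log2 titre with cohort, age and sex. It uses every participant, including those whose matched partner drops out. The cost is protocol wording and two degrees of freedom (38 to 36), under one point of power if the covariates turn out to be irrelevant. Age and sex are already recorded for matching.

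Keep the planned chi-square or Fisher test as the main test for the responder endpoints. Add an age- and sex-adjusted logistic model, penalised or exact, as a supporting analysis.

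In section 16.1, state whether matching is individual or by frequency. If pairs are formed, record a pair identifier and use any pair-based analysis only as a sensitivity analysis.

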**Feasibility and Assessment:**

**Incentives:** 1) Compensation for efforts; 2) Altruism; 3) Free FDA-approved flu vaccine **Challenges:** 1) Many individuals do not self-identify as having metabolic syndrome (may not know diagnosis); 2) Multiple visits within the first week; 3) Lengthy gap between 5th and 6th visit, which may result in attrition, 4) Participants must have untreated metabolic syndrome.

**Issues relevant to rapid accrual:** *Availability of the target population:* A previous study that recruited a similar population (JWA-0786) required prescreening 325 individuals for the investigator to enroll 28 participants across the span of 2 years. The age upper limit of the current study, age 50, limits the eligible population. A NHLBI publication of prevalence by age group of metabolic syndrome of participants in the HUNT2 study suggests that the eligible population will increase (+30% for men, +40% for women) by including the 50-59 year old age group. A feasibility query of the Research Participant Repository reveals 17 potentially eligible volunteers of age 18-50, as well as an additional 22 potentially eligible volunteers aged 51-59. These volunteers are predominantly male due to restrictions of prior studies. *Study burdens:* Another study (TWA-0804) enrolled healthy volunteers to receive FDA-approved vaccines, with a similar duration and shorter between-visit follow-up period; that study enrolled 86 on-study of whom 15 dropped out before the 3 month final visit. *Time Constraints:* Due to vaccination and multiple visits in the first few days, Day 0 visits cannot occur on Fridays. Also, the flu season is limited; interest in the flu vaccine will likely wane by March so the enrollment window is brief.

**Projected enrollment timeline:** Recruitment initiation will begin as soon the study receives IRB approval, likely in the first or second week of November. The investigator's target of completing accrual by April 2016, which would allow for 5-6 months achieving complete study enrollment. This would require the enrollment of 10 participants (5 metabolic syndrome and 5 age matched controls) per month. The study requires 2 screening visits (1 week start-up lag). The enrollment timeline is ambitious, even assuming a steady flow of participants and likely only feasible using the Repository population and potentially expanding the age range. Based on previous recruitment experience of this population, CRROSS would predict 12- 15 months for study accrual, however given ResearchMatch and Repository resources, 6 months is ambitiously feasible.

**Recruitment Implementation:**

**Advertising development and placement-** CRROSS will develop and send out the IRB approved campus email to recruit individuals on campus. Internet outlets will include craigslist.com, centerwatch.com, rucares.org, researchmatch.org, and others as appropriately identified. **Local newspapers-**advertisements may be placed in local newspapers (i.e., Metro). **Centralized Call Management** – CRROSS will work with the research team to develop a protocol-specific pre-screening script based on IRB approved protocol eligibility criteria to prescreen volunteers who call [name]. Potentially eligible candidates will be passed onto the study team for further screening. CRROSS staff will also call volunteers based on Repository queries described above. Research teams are responsible to provide timely updates on pre/screening outcomes (through iRIS, etc.) to keep CRROSS strategies on target. **Research Volunteer Repository Database** – The investigator has agreed to associate protocol UAN-**REDACTED**48, the Research Volunteer Repository Protocol, enabling the CRSO to query the existing volunteer database to identify a list of potential volunteers who have agreed to be contacted for future studies and who meet basic eligibility criteria. The CRROSS will contact potential volunteer as allowed to determine interest and will refer eligible and interested volunteers to the study coordinator/investigator. In parallel, the research team will seek and document the granting or denial of permission to contact volunteers about future studies.

**Compensation plan:**

Total compensation: \$300

Screening	Visit 1	Visit 2	Visit 3	Visit 4	Visit 6
Visit 2					
\$20	\$40	\$50	\$50	\$60	\$80

**Unscheduled Study Visits:**

- Additional study visits will be compensated \$25 per visit for bloodwork taken in the event of abnormal or missing labs.

### 16.2 \*From the date of final IRB approval, how long will it take to complete enrollment of the study?

- 6 Months
- 12 Months
- 18 Months
- 24 Months
- More than 2 years (specify in years)

### 16.3 This Study

- Involves an intervention or comparison and a defined enrollment target
- Is a natural history study with expected annual enrollment over many years
- Is an exploratory mechanistic study
- Other

### 16.4 This Study will enroll:

- Healthy volunteers
- Individuals affected with a specific disease/disorder

Individuals affected with a specific disease/disorder

Both

**16.5 \* Do you plan on using the Research Participant Repository (RKO-0648) ?**

Yes  No

**16.6 \* Are you screening or recruiting from or through a record review of an existing patient database of a healthcare provider?**

Yes  No

**16.7 \* Please describe how the Recruitment Plan addresses recruitment of the volunteers consistent with the demographics of the condition under study:**

CRROSS staff will recruit participants to match the racial and ethnic diversity of this study population. The demographics of the RKO-0648 repository have been consistently similar (2009-2013) to the demographics reported in the NYC 2010 census. Through our plan to utilize our call management service and query the RKO-648 repository, we anticipate being able to enroll participants who match the disease demographics projected in the application.

**16.8 \* Do you plan to advertise directly to potential volunteers? (As opposed to relying on practitioner referrals or flyers to practitioners)**

Yes  No

**16.9 \* Do you plan to use the free, web-based volunteer registry, ResearchMatch.org, as a recruitment tool?**

Yes  No

**17.0 Research Participant Repository (RKO-0648)**

**17.1 This protocol, will be linked with the Research Volunteer Screening/Recruitment Data Repository run by the Recruitment staff and the Clinical Research Support Office (protocol RKO-0648-1008).**

In order to participate in the generation of the Repository the PI will enter into a Collector/Collaborator agreement regarding the Repository. The role of Collector/Collaborator is to contribute to the Repository the name, contact and demographic information, recruitment referral information, and screening outcome information, as well as appropriate protocol specific screening information, of volunteers who are screened by telephone or in person for entry into the protocol regardless of the screening outcome. In addition to screening volunteers for the PI's current study, verbal consent will be obtained from the volunteers regarding their willingness to be contacted in the future about possible additional research studies. This permission may be obtained by the Recruitment office staff through the central Call Center. If the PI receives calls directly from participants for initial prescreening, then the PI is responsible for collecting the required information and conveying it to the Recruitment staff for data entry. The consent or withholding of permission will be recorded in the Repository as will the name of the person who obtained the permission. A volunteer's permission or declination will not affect their eligibility for my current protocol, or future protocols. The Recruitment staff of the Clinical Research Support Office may gather the Repository information and request the verbal consent of the volunteer for re-contacting on my behalf as part of our recruitment plan.

In order to benefit from the Repository, the PI will enter into a Recipient/Collaborator agreement with the Repository. The Recipient/Collaborator may receive from the Repository pre-screened lists of potentially eligible subjects for his/her study as a means to facilitate recruitment. The Recruitment staff will prepare the Repository queries according to the protocol eligibility requirements and available Repository information, and may re-affirm permission to re-contact volunteers as necessary. The PI may use the information and names in the list from the Repository only for the current study and may not save the list to use for a future study of his/her own, nor may he/she share the list with colleagues for other studies."

**18.0 Utilization of ResearchMatch.org**

**18.1 Utilization of ResearchMatch.org for Recruitment**

**Basic information regarding this tool:**

- ResearchMatch.org is a national electronic, web-based recruitment tool that was created through the Clinical & Translational Science Awards Consortium in 2009 and is maintained at Vanderbilt University. There is no cost for researchers at participating institutions in the ResearchMatch.org Network to use ResearchMatch.org. The Vanderbilt IRB provides oversight for ResearchMatch.org as a recruitment tool and this has been documented within the ResearchMatch.org IRB Letter of Understanding which was executed by [name] in October, 2009. However, individual requests to use ResearchMatch.org as a recruitment tool must be submitted to this institutions' IRB.

**Registration:**

- This recruitment tool may be utilized once the PI or research staff registers for recruitment access through ResearchMatch.org and the Institutional Liaison provides approval.
- The ResearchMatch.org Institutional Liaison will review the study information and evidence of IRB approval. He/she will set the researcher's expiration date to mirror that of the study's IRB approval.

**Search Capability:**

- After being granted recruitment access, the researcher can search for appropriate matches amongst the non-identifiable ResearchMatch.org Volunteer profiles in the system. He/she can enter study inclusion/exclusion criteria in the ResearchMatch.org Search Builder which will yield a list of potential matches to the study's criteria.

#### Contacting ResearchMatch.org Volunteers:

- Once yielding a list of potential matches (ResearchMatch.org Volunteers), the researcher will send out IRB-approved content that will be the initial recruitment message that these volunteers receive about the study through ResearchMatch.org. The study's recruitment message will be inserted into the standard ResearchMatch.org electronic notification that informs possible matched Volunteers that he/she has been identified as a potential match for the study. The secure ResearchMatch.org clearinghouse will route this standard ResearchMatch.org email notification. These potential matching volunteers will have the option of replying yes, no, or not respond through a set of quick links available in this notification to the study announcement. **THE CONTACT MESSAGE WILL NOT INCLUDE THE STUDY'S DIRECT CONTACT INFORMATION (e.g. EMAIL, PHONE).** By responding yes, the Volunteer has authorized ResearchMatch.org to release his/her contact information to the researcher. The researcher will be responsible for managing this contact information as called for by this IRB-approved study protocol.

#### Study Management in ResearchMatch.org:

- Researchers (and the Liaison) can view information regarding his/her study's status in ResearchMatch.org (e.g. number of volunteers contacted for the study via ResearchMatch.org to date, response rate of volunteers, etc.). ResearchMatch.org will also be collecting aggregate data regarding the status of ResearchMatch.org volunteers within the study. Volunteers consent to this within the ResearchMatch.org Volunteer Agreement. This information will allow the researcher to indicate where the Volunteer currently stands within the recruitment process and thus will help the researcher monitor the utility and effectiveness of using this resource (e.g. Did not contact, Not eligible, Enrolled, Completed, etc.).

